5.3.3 Rescue Medications

Treatment of individual allergic reactions during OIT therapy will be with either an antihistamine and/or epinephrine, along with IV fluids, albuterol, and corticosteroids as indicated. Participants and parents are likely to have self-injectable epinephrine but for those who do not, self-injectable epinephrine will be prescribed. Participants will be trained in proper use of self-injectable epinephrine and will be able to demonstrate proper technique. All subjects will be given a food allergy action plan to follow while in this study.

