6.7.3 Build-up

After the initial dose escalation day, the participant will return to the research unit the next morning for a dose of the highest tolerated dose from the initial escalation day. This dose will be at least 3 mg peanut flour (1.5 mg peanut protein) and will be maximum 12 mg peanut flour (6 mg peanut protein). The dosing escalation will be incremental based on previous OIT studies.

The first daily dose of peanut will be given in the clinical research unit to ensure there are no ill effects of the once-daily dosing. Thereafter, the daily dose will be given at home. Every 2 weeks (12 to 21 days), the participant will return to the research unit for a dose escalation. During observed dose escalation visits, if there are no symptoms after a 30 minute-to-2 hour observation period, the subject will be discharged. The observation time period is dependent on the length of time on the study, the subject's previous dosing history for the immediate past 2 weeks and throughout the study, and number of missed doses during the past 2 weeks.

With observed dose escalations, vital signs will be performed prior to dosing, before discharge, and anytime moderate symptoms occur. Physical assessment will be performed at each of these set times and at 30 minute intervals while the subject is in the clinical research unit for dose escalations. If symptoms occur that do not require treatment, the participant will be observed until they resolve. If symptoms occur that require diphenhydramine or albuterol, the subject will be observed for a minimum of 2 hours or until the participant's symptoms resolve. If symptoms occur that require epinephrine, the participant will be observed a minimum of 4 hours or until the participant's

symptoms resolve. If symptoms do not fully resolve after 4 hours or if new symptoms occur, the participant will be transferred to a hospital and observed overnight at the physician's discretion.

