If a participant has a dose escalation in the clinical research center without symptoms, the action should be to continue per protocol with daily home dosing of the tolerated dose with the next escalation visit to the clinical research center 2 weeks later. If the participant only experiences oral/pharyngeal pruritus during the administration of the daily dose, then the same dose can be repeated the next day at home and continued throughout the interval unless other symptoms begin to develop (see below).

For *mild symptoms*, defined as —

- skin — limited or localized hives/swelling, skin flushing or pruritus
- respiratory — rhinorrhea or sneezing, nasal congestion, occasional cough, throat discomfort
- GI — mild abdominal discomfort or minor episode of vomiting

The action should be to either repeat the dose the next day (day 2) at home or to have the participant return to the clinical research center the next day (day 2) for a repeat of the previous day's dose or the last tolerated dose (at the physician's discretion). If the dose is tolerated, then the participant will

continue on that dose and return at the normal interval. If the dose causes mild symptoms again, then the participant may return to the clinical research center (day 3) and be given the last tolerated dose or a 1-2 step dose reduction. If tolerated, the participant will continue on this dose for the normal time interval. If mild symptoms recur, a 1-2 step reduction would be administered the next day (day 4). If tolerated then that dose would be continued for 2 weeks. If not tolerated, consultation with the Protocol Chair would be indicated.

For *moderate symptoms*, defined as—

- skin — systemic hives or swelling
- respiratory — throat tightness without hoarseness, persistent cough, wheezing without dyspnea
- GI — persistent moderate abdominal pain/cramping/nausea, increased vomiting

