The action should be to have the subject return to the clinical research center the next day (day 2) for dosing with the previous day's dose or the last tolerated dose under observation. If the dose is tolerated, the participant will continue on that daily home dose for the normal time interval per protocol. If the subject does not tolerate this dose, the participant should receive the last tolerated dose or a 1-2 step dose reduction (day 3) in the clinical research center or at home if the planned dose was previously tolerated. If this dose is tolerated, it will be continued as the daily home dose for the normal time interval, then escalation attempted in the clinical research center as noted below. If this dose is not tolerated, then the next dose will be a 1-2-step reduction in dosing, and the dose will be given at the clinical research center (day 4). If this next dose is not tolerated, then a discussion with the Protocol Chair or Co-Chair will ensue to make a decision about whether to continue the subject on active treatment in the study.

For more *severe symptoms*, defined as —

- respiratory — laryngeal edema, throat tightness with hoarseness, wheezing with dyspnea
- GI — significant severe abdominal pain/cramping/repetitive vomiting
- neurological — change in mental status
- circulatory — hypotension

The action should be to treat the participant, and at the physician's discretion either: (1) have them return to the clinical research center the next day (day 2) for dosing with a two-step reduction in dose under observation or (2) discontinue them from the active treatment. If the participant tolerates the dose reduction, then they will remain on that dose for 2 weeks and then return to the clinical research center for the dose escalation. A discussion with the Protocol Chair or Co-Chair may ensue to make a decision about whether to continue the subject on active treatment in the study.

For a completed dose escalation with no symptoms, participants should be observed for a minimum of 30 minutes. For mild symptoms, subjects should have a 1-2 hours post-protocol observation period. For moderate to severe symptoms, the observation period should be at least 4 hours and up to 24 hours based on symptoms and treatment regimen needed to stabilize.

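### Section 6.7.3 sets post-dose observation twice, by treatment and by symptom grade, and the two disagree for build-up reactions not treated with epinephrine

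*Combined protocol and SAP*

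**What the plan says.** Section 6.7.3 covers observed dosing in the build-up phase and gives two observation schemes.

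The paragraph on vital signs at observed dose escalations goes by **treatment given**:
- No treatment: "If symptoms occur that do not require treatment, the participant will be observed until they resolve".
- Antihistamine or bronchodilator: "If symptoms occur that require diphenhydramine or albuterol, the subject will be observed for a minimum of 2 hours", or until resolution.
- Epinephrine: "If symptoms occur that require epinephrine, the participant will be observed a minimum of 4 hours", or until resolution.

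The paragraph after the actions for severe symptoms goes by **grade**:
- Mild: "For mild symptoms, subjects should have a 1-2 hours post-protocol observation period".
- Moderate or severe: "For moderate to severe symptoms, the observation period should be at least 4 hours and up to 24 hours", with the place in that range depending on symptoms and on the treatment needed.

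The same section lists as moderate respiratory symptoms "throat tightness without hoarseness, persistent cough, wheezing without dyspnea". Section 5.3.3 (Rescue Medications) says "Treatment of individual allergic reactions during OIT therapy will be with either an antihistamine and/or epinephrine", with albuterol among the additional treatments as indicated.

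**The concern.** Treatment and grade are different ways of classifying the same reaction, and one child can be classified by both at once. Wheezing without dyspnea is graded moderate, and Section 5.3.3 allows a reaction to be managed without epinephrine. A wheezing child given albuterol therefore falls under a 2-hour minimum in one paragraph and a 4-hour minimum in the other.

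The instruction concerns the safety of children enrolled at 12 to under 48 months of age in a multi-center trial. If sites work from different paragraphs, they may discharge children at different times after the same reaction. A monitor would also have no stated basis for deciding which paragraph a discharge should be checked against.

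**Working it through.** No sample size, power or error rate is involved, so the check is a side-by-side reading. It assumes that both periods run from the same starting point, because the section does not define a common clock.

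| Reaction | Treatment rule | Grade rule | Result |
|---|---|---|---|
| Moderate or severe, diphenhydramine or albuterol only | minimum 2 h, or until resolution | at least 4 h | Disagree: 4 - 2 = 2 h |
| Moderate, untreated | until resolution, no minimum | at least 4 h | Disagree whenever resolution comes before 4 h |
| Mild, diphenhydramine or albuterol | minimum 2 h, or until resolution | 1-2 h | Disagree by up to 2 - 1 = 1 h, in the other direction |
| Moderate or severe, epinephrine | minimum 4 h, or until resolution | at least 4 h | Minimums agree |

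1. **First row.** Between hours 2 and 4, a child whose symptoms have resolved meets the treatment rule for discharge and does not meet the grade rule.
2. **Second row.** The treatment rule sets no time floor, so the size of the gap depends on how fast symptoms clear.
3. **Third row.** Discharge at 1 hour is inside the grade rule's 1-2 hours but short of the treatment rule's 2-hour minimum. The treatment rule is now the longer one, so following only one paragraph throughout does not satisfy both.
4. **Fourth row.** The stated minimums are the same. The *or until* wording in the treatment rule could be read as allowing discharge before 4 hours if symptoms clear early. That is a looser point, and the finding does not rest on it.
5. **Precedence.** Neither paragraph cross-refers to the other, and nothing in the section says that the longer time applies. The verbs do not settle it: the treatment rule says what *will* be done and the grade rule what *should* be done.
6. **Comparison within the protocol.** Section 6.7.2 (Initial Dose Escalation) sets its observation period by grade alone. The double scheme appears in build-up.
7. **Carry-over.** Section 6.7.4 applies the build-up dosing rules to symptoms in maintenance. The ambiguity may extend there, if those rules are taken to include observation times.

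**The case against.** The strongest reply is that these are two floors, not two incompatible commands. A minimum of 2 hours does not authorize discharge at 2 hours if another provision requires longer. Four hours of observation meets both minimums for a moderate reaction, and the grade rule makes no exception for reactions treated without epinephrine. On this view only a cross-reference is missing.

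Much of that stands. The two minimums can be met together, and a reader should not infer that the protocol as a whole permits discharge of a moderate case at 2 hours. But the reply depends on a longest-time-governs principle that the section does not state. The treatment paragraph also reads as a complete discharge rule, and which paragraph is longer changes between moderate and mild reactions.

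A second reply is that the grade rule already takes account of the treatment needed. It does, but only in placing the child within the range of 4 to 24 hours. That wording does not lower the 4-hour floor.

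Two stronger readings are tempting, and the documents do not support them:
- **Recording of adverse events.** A reader might infer that earlier discharge changes where a late symptom is recorded. Section 8.3.2.2 sorts events by time since dosing, expectedness, relatedness and a list of named events. The place where the symptom is seen is not a criterion.
- **Number of visits affected.** A reader might count an escalation for each of the 144 planned children every two weeks through week 28. Table 1 shows otherwise: the 6 mg column reaches 2000 mg at week 24 and the 3 mg column at week 26, and only the 1.5 mg column still has a scheduled increase at week 28. Section 6.7.3 also allows the week 28 visit to be by telephone in one scenario. Section 9.3 assigns 48 of the 144 to placebo.

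**Conclusion.** The two observation schemes in Section 6.7.3 disagree for reactions not treated with epinephrine, and the section does not say which governs. The minimums differ by 2 hours for a moderate or severe reaction given only diphenhydramine or albuterol, and by up to 1 hour in the opposite direction for a mild reaction given the same drugs. For an untreated moderate reaction, one rule has a 4-hour floor and the other has none. These figures assume a common starting point for both periods.

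The point is minor in scale and concerns consistent safety conduct across sites. The documents give no frequency for such reactions, so the number of children affected cannot be estimated. Sample size, power, endpoints and analysis are not touched.

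**What to change.** The sponsor should reconcile the two paragraphs of Section 6.7.3 into one observation rule, stating which governs when the treatment given and the symptom grade point to different times. The same edit could settle the *or until* wording, say when the period starts, and say whether the rule carries into maintenance under Section 6.7.4. This review takes no position on which observation time is right.

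The cost is a change of protocol wording, which under Section 12.1 needs sponsor and IRB approval and submission to FDA before use. Depending on the rule chosen, some children may stay longer in clinic. No change to the statistical plan is needed.

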6.7.4 Maintenance

This phase consists of the subject receiving the daily dose of 4000 mg peanut flour (2000 mg peanut protein or highest tolerated dose) daily for at least 104 weeks at home. The participants will continue to follow an otherwise peanut-restricted diet.

Participants who did not reach the 4000 mg peanut flour (2000 mg peanut protein) dose during the build-up phase will continue at their highest tolerated dose, which will be at least 500 mg peanut flour (250 mg peanut protein).

A consistent time (within a 4-hour time period) will be recommended for home dosing, and it will be stressed that it is critical to take the dose every day. Participants will be informed to separate the dose by at least 12 hours. Participants will continue to take all their regularly prescribed medications consistent with the eligibility criteria for the protocol.

For any noted symptoms during the maintenance phase, the same study dosing rules for the build-up phase will be followed.

The participant will continue on daily OIT with return visits every 13 weeks.

6.7.5 Avoidance

After completion of 104 weeks of maintenance dosing and a 10 g blinded OFC to peanut flour (5 g peanut protein), participants will stop daily dosing. Participants will avoid consumption of peanut, either as a daily dose or as part of their regular diet for 26 weeks.

After 26 weeks of avoidance, participants will undergo a final 10 g blinded OFC to peanut flour (5 g peanut protein). Participants who do not have a clinical reaction to the challenge will receive an Open Food Challenge (OpFC) (See [Section 6.4.3](#)).

6.7.6 Post-Challenge

If participants do not have a clinical reaction during the OpFC at the end of avoidance, they will be allowed to consume peanut and will have one visit which will include peripheral blood sampling for mechanistic assays assessments.

Post-challenge will comprise 2 weeks.

6.8 MISSED DOSES AND DOSING DURING CONCURRENT ILLNESS

6.8.1 Missed Doses for Non-Compliance

Missed doses at any phase of the study can pose a significant risk to the enrolled subjects. The algorithm for missed consecutive doses is as follows:

- 1 dose — the next dose would be the current dose and could be given at home
- 2 doses in a row — the next dose would be the current dose and could be given at home
- 3 or 4 doses in a row — the next dose would be the current dose and would be given under observation in the clinical research unit
- 5 to 7 doses in a row— the next dose would be 75% of the current dose and would be given under observation in the clinical research unit
- 8 to 14 doses in a row — initiate the next dose as approximately 50% of the last tolerated dose. This would be done under observation in the clinical research unit.

After any dose reduction, dose escalation would occur in the clinical research unit with an escalation no sooner than weekly and no longer than every 4 weeks with dose increases of 1 dose level at each escalation. If symptoms occur, the dosing symptom rules in the build-up phase would apply. Study site staff will contact the investigator if 1 or 2 missed doses are due to an allergic reaction or symptom. Study staff will contact the investigator for all missed doses of 3 or more.

6.8.2 Management of Dosing During Concurrent Illness

If a participant has gastroenteritis, nausea and vomiting, upper-respiratory infection, active wheezing, fever greater than 100.5° C, or other similar illness, the parent should hold the dose and call the study center for instructions regarding dosing. Depending on the severity of the illness, the study center may instruct the parent to hold dosing for one or more days. Reinitiating dosing will be according to the algorithm described in [Section 6.8.1](#).

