4. SELECTION AND WITHDRAWAL OF PARTICIPANTS

4.1 INCLUSION CRITERIA

Patients must meet *all* of the following criteria to be eligible for this study:

1. Age 12 months to less than 48 months, either gender.
2. Clinical history of peanut allergy or avoidance of peanut without ever having eaten peanut.
3. Serum IgE to peanut of ≥ 5 kUA/L determined by UniCAP™.
4. Wheal ≥ 3 mm on skin prick test to peanut extract compared to a negative control.
5. A clinical reaction as defined in [Section 6.4.3](#) at or below ingestion of 1 g peanut flour (500 mg peanut protein) during screening blinded OFC.
6. Written informed consent from parent/guardian.

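### The fever threshold for holding a home dose (Section 6.8.2) is printed as 100.5 °C, which no child can reach; °F was evidently meant

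*Combined protocol and SAP*

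**What the plan says.** Section 6.8.2 (Management of Dosing During Concurrent Illness) gives parents a list of conditions that interrupt home dosing. It opens "If a participant has gastroenteritis, nausea and vomiting, upper-respiratory infection, active wheezing" and closes with "fever greater than 100.5° C, or other similar illness". For any of these, "the parent should hold the dose and call the study center for instructions regarding dosing". The center may then extend the hold, and dosing restarts under the missed-dose algorithm in Section 6.8.1.

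Fever is the only item with a numeric cut-off. The families applying the rule have very young children; the entry criterion in Section 4.1 is "Age 12 months to less than 48 months, either gender".

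**The concern.** A body temperature above 100.5 °C is impossible, so the one numeric trigger in a dosing-safety instruction cannot operate as written. The instruction is used at home, by parents, through build-up and a 104-week maintenance phase, at doses of up to 2000 mg of peanut protein a day (Sections 3.1 and 6.7.4).

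A number is given so that families and sites act alike. If the printed number is unusable, each reader has to supply another, and the choice matters in both directions:

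- A substitute that is too high means dosing a child through a fever.
- A substitute that is too low adds missed doses, which Section 6.8.1 itself treats as a hazard. Under that section, three or more consecutive missed doses bring the child back for observed dosing, and five or more also bring a dose reduction. Under Section 5.2, circumstances such as illness that require more than 14 consecutive missed days end therapy.

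**Working it through.** **Inputs.** The threshold is above 100.5 °C and the action is to hold the dose and call; both come from Section 6.8.2. The plan derives neither by calculation, so there is no planned figure to reproduce. The check is a unit conversion and a search for a correction elsewhere.

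**As printed.** °F = °C × 9/5 + 32, so 100.5 × 9/5 + 32 = 180.9 + 32 = **212.9 °F**. This is above the boiling point of water.

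**Read as Fahrenheit.** °C = (°F − 32) × 5/9, so (100.5 − 32) × 5/9 = 68.5 × 5/9 = **38.06 °C**. This is a plausible fever cut-off. The figure makes sense in one unit only.

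**Is it corrected elsewhere?**
- Section 6.3 lists temperature among the vital signs but sets no cut-off.
- The other temperatures in the protocol concern storage or thawing, for example 2 to 8 °C for the flour in Section 5.1.3.3. None supplies a clinical value.
- Section 6.8.2 is the only place with a fever threshold.

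**Could it come from reading the PDF?** This is unlikely. The unit is a letter in running prose with its degree sign intact. The extract-storage temperature in Section 5.1.2.3 shows that a degree sign can be garbled, but that kind of damage does not turn an F into a C.

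**How much of the rule is lost?** The list has six items: gastroenteritis, nausea and vomiting, upper-respiratory infection, active wheezing, fever, and other similar illness. One fails literally and five work. The gap is therefore fever accompanied by none of the named conditions and not treated as a similar illness.

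**Can the exposure be counted?** No. The documents give no rate of isolated fever. The planned peanut arm is 144 × 2/3 = 96 children and the placebo arm 144/3 = 48. The 96 is only an outer limit on who could take a peanut dose during such a fever; it does not estimate how many would.

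**The case against.** The strongest reply is that the slip corrects itself. No parent, nurse or physician would take 100.5 °C for a body temperature, so in practice everyone reads °F and the rule works as intended. The rule also has backstops:

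- The catch-all covers a febrile illness.
- Section 6.7.3 provides an on-call physician day and night.
- Section 6.1.2 allows unscheduled visits for dose observation.
- Section 6.8.1 controls how dosing restarts.

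The same instruction applies to both blinded arms, and no endpoint, eligibility criterion, stopping rule or analysis uses the threshold. Nothing in the documents shows that the error reached any material given to families. On this view it is a typographical slip rather than a fault of calculation, and quoting arm sizes makes it look more quantified than it is.

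Most of this stands, and it is why the point is rated minor. The error is one of unit, the arm sizes measure no effect, and no harm is shown. None of it makes the printed threshold correct. A safety rule should not depend on each reader quietly replacing its only number, and the family dosing sheets are not among the documents, so whether they repeat the error is unknown.

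**Conclusion.** The concern holds, as a minor point and with high confidence. The fever criterion in Section 6.8.2 cannot be met as written (212.9 °F), and nothing else in the documents repairs it. That Fahrenheit was intended is an inference, but the only sensible one, since the same figure in °F gives 38.06 °C.

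The practical effect is probably small. It is confined to isolated fever under a literal reading, or to readers substituting different cut-offs. The sample size of 144, the power and the primary analysis are untouched.

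**What to change.** In Section 6.8.2, replace the threshold with: fever greater than 100.5 °F (about 38.1 °C), after the sponsor confirms that this is the intended value. Give both units, because the protocol's other temperatures are in Celsius. Keep the word *about* and let the Fahrenheit figure govern: 38.1 °C converts back to 38.1 × 9/5 + 32 = 100.58 °F, so the two are not exactly equal.

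Then check that the family and site dosing instructions carry the same figure. The cost is a one-line protocol correction and that check, with no change to design or analysis.
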